14.6	Future Use of Stored Specimens	57
15	Data Handling and Record Keeping	58
15.1	Data Management Responsibilities.....	58
15.2	Data Capture Methods.....	58
15.3	Types of Data	58
15.4	Timing/Reports	59
15.5	Study Records Retention	59
15.6	Protocol Deviations.....	59
16	Publication Policy	60
17	Literature References.....	61
	APPENDIX A – Schedule of Evaluations.....	62

LIST OF FIGURES AND TABLES

Figure 1: Study Schematic	X
Table 1. Ordinal Outcome	16
Table 2: Severity of Cough.....	17
Table 3. Solicited Events Grading	17

LIST OF ABBREVIATIONS

AE	Adverse Event/Adverse Experience
ARLG	Antibiotic Resistance Leadership Group
ATP	According-to-Protocol
CAP	Community Acquired Pneumonia
CC	Complete Case
CFR	Code of Federal Regulations
CMS	Clinical Materials Services
DHHS	Department of Health and Human Services
DMID	Division of Microbiology and Infectious Diseases, NIAID, NIH, DHHS
DOOR	Desirability of Outcome Ranking
DSMB	Data and Safety Monitoring Board
eCRF	Electronic Case Report Form
ED	Emergency Department
EHR	Electronic Health Record
FDA	Food and Drug Administration
FWA	Federalwide Assurance
GCP	Good Clinical Practice
HIPAA	Health Insurance Portability and Accountability Act
ICH	International Conference on Harmonisation
ICMJE	International Committee of Medical Journal Editors
IDES	Internet Data Entry System
IDSA	Infectious Diseases Society of America
IEC	Independent or Institutional Ethics Committee
IND	Investigational New Drug Application
IRB	Institutional Review Board
ISM	Independent Safety Monitor
ITT	Intention-to-Treat
MOP	Manual of Procedures
NIAID	National Institute of Allergy and Infectious Diseases, NIH, DHHS
NIH	National Institutes of Health
OHRP	Office for Human Research Protections
PI	Principal Investigator
QA	Quality Assurance
QC	Quality Control
RADAR	Response Adjusted for Days of Antibiotic Risk
SAE	Serious Adverse Event/Serious Adverse Experience
SDCC	Statistical and Data Coordinating Center
SUSAR	Suspected Unexpected Serious Adverse Reaction
US	United States
USP	United States Pharmacopeia

PROTOCOL SUMMARY

Title:	A Phase IV Double-Blind, Placebo-Controlled, Randomized Trial to Evaluate Short Course vs. Standard Course Outpatient Therapy of Community Acquired Pneumonia in Children (SCOUT-CAP)
Phase:	IV
Population:	Approximately 400 subjects aged 6-71 months of age with community acquired pneumonia (CAP)
Description of Sites/Facilities Enrolling Participants:	5 to 10 US outpatient sites
Study Duration:	25 months
Subject Participation Duration:	~1 month after beginning antibiotic therapy
Description of Agent or Intervention:	Oral suspensions of amoxicillin, amoxicillin-clavulanate, cefdinir and matching placebos
Objectives:	
Primary:
 
1. To compare the composite overall outcome (Desirability of Outcome Ranking, DOOR) among children 6-71 months of age with CAP assigned to a strategy of short course (5 days) vs. standard course (10 days) outpatient beta-lactam therapy at Outcome Assessment Visit #1 (Study Day 8 +/- 2 days) 
Secondary:
 
1. To compare the composite overall outcome (DOOR) among children 6-71 months of age with CAP assigned to a strategy of short course (5 days) vs standard course (10 days) outpatient beta-lactam therapy at Outcome Assessment Visit #2 (Study Day 22 +/- 3 days)2. To compare the resolution of symptoms (a component of DOOR) among children 6-71 months of age with CAP assigned to a strategy of short course (5 days) vs standard course (10 days) outpatient beta-lactam therapy at Outcome Assessment Visits #1 and #2

3. To compare the clinical response (a component of DOOR) among children 6-71 months of age with CAP assigned to a strategy of short course (5 days) vs standard course (10 days) outpatient beta-lactam therapy at Outcome Assessment Visits #1 and #2
4. To compare solicited events (a component of DOOR) among children 6-71 months of age with CAP assigned to a strategy of short course (5 days) vs standard course (10 days) outpatient beta-lactam therapy at Outcome Assessment Visits #1 and #2
5. To compare medically attended visits to Emergency Departments (ED) or outpatient clinics, hospitalizations, surgical procedures, and receipt of non-study systemic antibiotics (components of the clinical response) among children 6-71 months of age with CAP assigned to a strategy of short course (5 days) vs standard course (10 days) outpatient beta-lactam therapy at Outcome Assessment Visits #1 and #2

Exploratory:

1. To examine the robustness of results of DOOR comparisons when increasing the threshold in assigning different ranks due to differing numbers of days of antibiotic use from a one day difference to a two, three, four, or five day difference.

[figure not shown]
Description of Study Design:

Double-Blind, Placebo-Controlled, Randomized Trial

Estimated Time to Complete Enrollment:

Approximately 24 months

Figure 1: Study Schematic

2 BACKGROUND INFORMATION AND SCIENTIFIC RATIONALE

2.1 Background Information

The World Health Organization estimates 156 million cases of pneumonia occur annually in children <5 years of age.¹ In the United States (US), an estimated 1.5 million ambulatory visits for community-acquired pneumonia (CAP) in children occur annually.² Hospitalizations for CAP in children have decreased after the introduction of pneumococcal conjugate vaccine.³ Further, in a pneumonia etiology study of >2500 children hospitalized with CAP in 3 US cities between 2010 and 2012, viral pathogens accounted for >70% of detections, while bacteria were identified in <20%.⁴ However, ambulatory visits have not decreased, and pediatric CAP remains a very common infection for which antibiotics are generally prescribed.²

A 2011 Infectious Diseases Society of America (IDSA) guideline for management of CAP in children provides recommendations for antibiotic therapy.⁵ Regarding the treatment duration for beta-lactam antibiotics, the guideline states “courses of 10 days have been best studied.” Two studies conducted in resource-poor settings found no difference in outcomes between 3 vs. 5 days of oral therapy or 3 days of oral therapy vs. placebo for non-severe pneumonia.^{6,7} However, these studies likely included many subjects with viral infection because substantial proportions had no radiographic findings or included children with wheezing. While stating “shorter courses may be just as effective,” the IDSA guideline concluded there was insufficient evidence to recommend short course therapy.⁵ The guideline identified clinical trials that provide information on the “shortest duration of therapy to decrease the development of antimicrobial resistance and the risk of antimicrobial toxicity” as a priority for future research.⁵

2.2 Rationale

In 2014, a randomized trial of short vs. standard course therapy in young children in Israel with CAP suspected to be of bacterial origin found a higher rate of treatment failure (40%) in subjects treated for only 3 days vs. subjects treated for 5 or 10 days.⁸ The study was underpowered to detect a difference in treatment failure between subjects treated for 5 vs. 10 days, but treatment failure did not occur in either group.

The proposed study will test the effectiveness of short (5-day) vs. standard (10-day) course therapy in children who are diagnosed with CAP and initially treated in outpatient clinics, urgent care facilities, and emergency departments. The study will specifically address whether short course therapy is superior to standard therapy among children that have clinically improved since diagnosis. If superior to standard course therapy, short course therapy could reduce antibiotic exposure among young children. We will use a study methodology similar to the SCOUT Study (“Short Course Therapy for Urinary Tract Infections in Children”)—a randomized, double-blind, placebo-controlled non-inferiority trial of short course antimicrobial therapy for urinary tract infection in children sponsored by NIAID through the “Targeted Clinical Trials to Reduce the Risk of Antimicrobial Resistance” initiative. However, the SCOUT-CAP trial will use a superiority study design using an ordinal composite overall outcome (Desirability of Outcome Ranking, DOOR, see 3.2.1 Primary Outcome Measures)—to test the hypothesis that short

course (5 day) therapy is superior to standard course (10-day) beta-lactam therapy in children who have experienced early clinical improvement of pneumonia.

2.3 Potential Risks and Benefits

2.3.1 Potential Risks

The potential risk of short course therapy is that clinical outcomes may not be equivalent to standard course therapy. Specifically, the percent of children with adequate clinical response (or in this case, no relapse of illness) may be lower in children receiving short course therapy. Adequate clinical response can be defined as resolution or substantial improvement in clinical signs and symptoms (e.g., fever, cough, respiratory rate, work of breathing) and the lack of need for additional antibiotic therapy, additional contacts with the health care system, or surgical procedures for worsening pneumonia. The magnitude of this risk is not well established, although a study from Israel suggests it is small⁸; nevertheless, this degree of risk will be evaluated during this trial.

2.3.2 Known Potential Benefits

If, as assessed by the primary outcome, short course therapy is superior to standard course therapy, short course therapy will reduce antibiotic exposure among children with CAP. The potential benefits of reduced antimicrobial exposure involve benefits both to the individual child and the population as a whole.

Potential benefits to the individual child include a simpler course of therapy, a lower risk of an adverse event associated with antibiotic therapy (e.g., antibiotic associated diarrhea, *Clostridium difficile* infection) and a lower risk of becoming colonized with antibiotic resistant bacteria.

Potential benefits to the population include a lower prevalence of colonization with pathogenic antibiotic resistant bacteria among children treated for CAP. Since these bacteria are transmissible, a lower prevalence of colonization among children treated for CAP confers a potential lower risk of colonization among all persons in the population, including children and adults regardless of whether they are treated with antibiotics.

3 OBJECTIVES

3.1 Study Objectives

Primary:

1. To compare the composite overall outcome (Desirability of Outcome Ranking, DOOR) among children 6-71 months of age with CAP assigned to a strategy of short course (5 days) vs standard course (10 days) outpatient beta-lactam therapy at Outcome Assessment Visit #1 (Study Day 8 +/- 2 days)

Secondary:

1. To compare the composite overall outcome (DOOR) among children 6-71 months of age with CAP assigned to a strategy of short course (5 days) vs standard course (10 days) outpatient beta-lactam therapy at Outcome Assessment Visit #2 (Study Day 22 +/- 3 days)
2. To compare the resolution of symptoms (a component of DOOR) among children 6-71 months of age with CAP assigned to a strategy of short course (5 days) vs standard course (10 days) outpatient beta-lactam therapy at Outcome Assessment Visits #1 and #2
3. To compare the clinical response (a component of DOOR) among children 6-71 months of age with CAP assigned to a strategy of short course (5 days) vs standard course (10 days) outpatient beta-lactam therapy at Outcome Assessment Visits #1 and #2
4. To compare solicited events (a component of DOOR) among children 6-71 months of age with CAP assigned to a strategy of short course (5 days) vs standard course (10 days) outpatient beta-lactam therapy at Outcome Assessment Visits #1 and #2
5. To compare medically attended visits to Emergency Departments (ED) or outpatient clinics, hospitalizations, surgical procedures, and receipt of non-study systemic antibiotics (components of the clinical response) among children 6-71 months of age with CAP assigned to a strategy of short course (5 days) vs standard course (10 days) outpatient beta-lactam therapy at Outcome Assessment Visits #1 and #2

Exploratory:

1. To examine the robustness of results of DOOR comparisons when increasing the threshold in assigning different ranks due to differing numbers of days of antibiotic use from a one day difference to a two, three, four, or five day difference.

3.2 Study Outcome Measures

3.2.1 Primary Outcome Measures

The primary endpoint/outcome measure is the DOOR at Outcome Assessment Visit #1.

DOOR is defined as follows:

- I. Each subject is evaluated according to the ordinal composite outcome (See Table 1 below) and assigned an outcome rank ranging from 1-8.
- II. Desirability of Outcome Ranking (DOOR) is then assigned according to two rules:
 - (i) When comparing two subjects with different ordinal responses, the subject with a better ordinal response receives a higher rank.
 - (ii) When comparing two subjects with identical ordinal responses, the subject with fewer days of antibiotic use receives a higher rank.

The ordinal composite outcome involves an assessment of whether the subject has an adequate clinical response and whether they have experienced any solicited events as defined below.

Table 1. Ordinal Outcome

	Adequate clinical response¹ (Assessed at Outcome Assessment Visits #1 and #2)	Solicited events³ (Assessed at Outcome Assessment Visits #1 and #2)
1	Yes, with resolution of symptoms ²	None
2	Yes, with resolution of symptoms ²	Mild (Grade 1)
3	Yes, with resolution of symptoms ²	Moderate (Grade 2)
4	Yes, with resolution of symptoms ²	Severe (Grade 3)
5	Yes, with persistent symptoms of fever, tachypnea, or cough	None or any grade
6	No, with ED/clinic visit but no hospitalization	None or any grade
7	No, with hospitalization	None or any grade
8	Death from any cause	

¹Adequate clinical response is defined as the absence of a medically attended visit to an ED or outpatient clinic or hospitalization for persistent or worsening pneumonia that occurs after randomization and receipt of at least one dose of study drug.

- Persistent or worsening pneumonia is defined as receipt of a non-study systemic antibiotic for pneumonia or treatment for a complication of pneumonia, including drainage of pleural fluid, placement of a chest tube, video assisted thoracoscopic surgery, or thoracotomy procedures.
- Note: Receipt of a non-study antibiotic will not be regarded as satisfying this definition if it is related to a new diagnosis that is unrelated to the prior diagnosis of pneumonia.

²Resolution of symptoms is defined as the absence of all of the following:

- Oral, rectal, axillary, or tympanic temperature $\geq 38.3^{\circ}\text{C}$ (100.9°F), confirmed by repeat measurement after at least 15 minutes, in the 24 hours preceding the Outcome Assessment Visit or measured at the Outcome Assessment Visit, unless attributed to a new process that is unrelated to the prior diagnosis of pneumonia;
- Elevated respiratory rate (RR >50 breaths/minute for children <24 months of age and >40 breaths/minute for children 24-71 months of age) at the time of the Outcome Assessment Visit;
- Presence of cough grade 2 or 3 at the Outcome Assessment Visit, (defined in Table 2).

³Solicited events (Table 3) will be captured daily until Outcome Assessment Visit #2; thereafter, parents/legal guardians will report symptoms based on memory aid and medical interview by

study staff. For those with multiple solicited events, the ordinal response table will be based upon the most severe solicited event.

Table 2: Severity of Cough

Symptom	Mild (Grade 1)	Moderate (Grade 2)	Severe (Grade 3)
Cough	Occasional coughing (less than 4 times hourly)	Frequent coughing (4 or more times an hour), interferes with sleep)	Almost constant coughing (never free of cough), makes sleep nearly impossible

Table 3. Solicited Events Grading

Symptom	Mild (Grade 1)	Moderate (Grade 2)	Severe (Grade 3)
Irritability	More irritable or fussy than usual but can be consoled; no interference with smiling/playing	Irritability or fussiness that is difficult to console and interferes with smiling and playing	Irritability or fussiness that lasts for more than 4 consecutive hours in a 24 hour period or cannot be consoled
Vomiting	1 episode/day	2-3 episodes/day	≥4 episodes/day
Diarrhea	Looser than normal stools occurring 3-6 times/day	Looser than normal stools occurring >6 times/day	Bloody diarrhea, or diarrhea that requires medical intervention, laboratory testing, or hospitalization
Allergic Reaction	Localized rash or pruritus without rash	Diffuse rash (maculopapular or urticarial)	Generalized rash consistent with Stevens-Johnson Syndrome, erythema multiforme, or toxic epidermal necrolysis; anaphylaxis; or angioedema
Stomatitis	Oral lesions associated with parenteral report of mild oral discomfort	Oral lesions associated with difficulty swallowing, but able to eat and drink	Oral lesions associated with inability to swallow solids or liquids; requires medical intervention, IV fluids, or hospitalization
Candidiasis	Mild mucocutaneous candidiasis or diaper dermatitis, with no treatment or topical treatment only	Moderate mucocutaneous candidiasis requiring oral antimicrobial treatment	Severe mucocutaneous candidiasis; requires medical intervention, intravenous treatment, or hospitalization

3.2.2 Secondary Outcome Measures

Secondary outcome measures include:

1. DOOR at Outcome Assessment Visit #2.
2. Resolution of symptoms (a component of DOOR) at each outcome assessment visit, defined as the absence of fever, tachypnea, or cough of grade 2 or higher.

3. Adequate clinical response rates (a component of DOOR) at each outcome assessment visit, defined as the absence of a medically attended visit to an ED or outpatient clinic or hospitalization for persistent or worsening pneumonia that occurs after randomization and receipt of at least one dose of study drug.
4. Frequency of solicited events at each outcome assessment visit, as listed in Table 3.
5. Medically attended visits to ED or clinic; hospitalizations; surgical procedures; and receipt of non-study systemic antibiotics for persistent or worsening pneumonia (as defined above) at each outcome assessment visit
 - i. Individual event types (e.g., medical visits, hospitalizations, surgical procedures, and receipt of non-study systemic antibiotics) will be compared between treatment groups.
6. Medically attended visits to ED or clinic; hospitalizations; surgical procedures; and receipt of non-study systemic antibiotics for all causes at each outcome assessment visit
 - i. Individual event types (e.g., medical visits, hospitalizations, surgical procedures, and receipt of non-study systemic antibiotic) will be compared between treatment groups.

3.2.3 Exploratory Outcome Measures

1. DOOR at Outcome Assessment Visits #1 and #2, when increasing the threshold in assigning different ranks due to differing numbers of days of antibiotic use from a one day difference to a two, three, four, or five day difference.

4 STUDY DESIGN

This is a multi-center, randomized, double-blind, placebo-controlled, superiority clinical trial evaluating short course (5 day) vs. standard course (10 day) of oral beta-lactam antibiotic therapy (amoxicillin, amoxicillin-clavulanate, cefdinir) for treatment of CAP in children 6-71 months of age who have clinically improved prior to enrollment. The study will randomize approximately 400 enrolled subjects to one of the two study arms (approximately 200 children in each arm) in order to reach 360 subjects completing Outcome Assessment Visit 1. Subjects will be randomized (1:1) to receive either a standard course of the initially prescribed antibiotic (10 days) or a short course of the initially prescribed antibiotic (5 days) plus 5 days of matching placebo.

The study will recruit potential subjects from children who are diagnosed with CAP and who are initiated on oral beta-lactam therapy (amoxicillin, amoxicillin-clavulanate, cefdinir) by healthcare providers in EDs, outpatient clinics, and urgent care centers at the study sites. Day -5 is defined as the date on which oral beta-lactam therapy is initiated for a diagnosis of CAP. Potential subjects will be identified at any time following clinical diagnosis of pneumonia. These subjects will be assessed for eligibility and enrolled on Day -3 to -1 of their initially prescribed oral beta-lactam therapy. Subjects may also be enrolled on Day 1 (the first day of receipt of study agent) provided they have not yet received any doses of the healthcare provider-prescribed antibiotic therapy for that day.

A Schedule of Events is provided in Appendix A.

Visit 1: Enrollment Visit. Subjects who meet the eligibility criteria, and whose parent/guardian consents for participation in the study, will complete an Enrollment Visit on Day -3 to -1. Subjects satisfying the inclusion criteria with no exclusion criteria will be enrolled and randomized. Enrolled subjects will continue to receive the initially prescribed antibiotic through Day -1. The subjects' parents/guardians will be instructed to contact study personnel if their child develops fever or worsening respiratory symptoms (worsening cough, increased work of breathing, any other concerning symptoms in the parents' estimation) following enrollment.

Randomization: Enrolled subjects will be randomized to short vs. standard course therapy at a 1:1 ratio, with stratification by 1) age group (<24 months vs. 24-71 months), 2) initially prescribed antibiotic (amoxicillin vs. amoxicillin-clavulanate vs. cefdinir), and 3) treatment site (emergency department vs. outpatient clinic/urgent care facility).

Intervention: Subjects will continue on the initially prescribed antibiotic through Day -1, until they have completed 5 days (i.e., 5 scheduled doses of once daily medication, 10 scheduled doses of twice daily medication) of antibiotic therapy [e.g., if a subject takes the first dose of antibiotic in the afternoon of Day -5, the first dose of study agent would occur on the afternoon of Day 1, providing 10 total scheduled doses of a twice daily prescribed antimicrobial]. The first day of receipt of study agent will be Day 1. Subjects assigned to standard course therapy will receive 5 additional days (10 doses) of the same initially prescribed antibiotic, with standardized twice-daily dosing. Subjects assigned to short course therapy will receive 5 more days (10 doses) of a matching placebo. Both the study agent and placebo may appear different than the commercial formulation the child originally received. The placebo will appear indistinguishable in

color, taste, thickness, and consistency as the active antibiotic the child would otherwise receive in the study. The study product will be labeled with a numerical code that masks site investigators, site staff, parent(s)/guardian(s) and children to the formulation.

Follow-up and Assessment of Endpoints: Subjects will be scheduled for the following assessment visits:

Visit 2: Outcome Assessment Visit #1, Day 6 to 10 (1-5 days after completing the study agent). Subjects will be evaluated for the components of the composite overall outcome, which include the adequacy of the subject's clinical response; persistence of symptoms of fever, tachypnea, or cough; the occurrence of any solicited events; and the duration of antibiotic therapy (both study product/placebo and any additional oral or parenteral antibiotic therapy prescribed by study or non-study providers).

Visit 3: Outcome Assessment Visit #2, Day 19 to 25 (14-20 days after completing the study agent). Subjects will be evaluated for the components of the composite overall outcome, which include the adequacy of the subject's clinical response; persistence of symptoms of fever, tachypnea, or cough; the occurrence of any solicited events; and the duration of antibiotic therapy (both study product/placebo and any additional oral or parenteral antibiotic therapy prescribed by study or non-study providers).

Subjects who are identified as having an inadequate clinical response prior to Outcome Assessment Visit #1 will be asked to complete Outcome Assessment Visits #1 and #2 in order to evaluate the occurrence of any solicited events and the duration of antibiotic therapy (both study product/placebo and any additional oral or parenteral antibiotic therapy prescribed by study or non-study providers).

Subjects will be invited to contribute oropharyngeal and stool specimens at specified times throughout the study for future use (see Appendix A, Schedule of Events). Additional informed consent will be obtained for future use sample collection.

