- Subjects will be provided with a memory aid and other study-related materials to record daily temperature, solicited events, concomitant medications, presence of cough, and daily dose administration. Parents will be instructed that any temperatures over 100.9°F should be repeated 15 minutes later in the same manner as the initial temperature. Study staff will instruct the parent/guardian to complete the memory aid in order to document adherence and to bring the medication bottle with them to the Outcome Assessment Visit #1. Study staff will also review the memory aid used to assess specific, solicited events;
- Collection of a throat swab specimen if contributing future use samples;
- Dispense containers for collection of a stool specimen, if participating in future use portion of the study.

Since the Enrollment Visit will occur during Day 3-5 of treatment (Day -3 to -1), the subject will be instructed to complete the originally prescribed medication through Day -1 (after receipt of the last dose of the originally prescribed medication on the fifth consecutive calendar day of treatment) and to start study product on Day 1.

Parents will be educated at the time of their child's enrollment in the study about prompt and adequate treatment for recurrence of symptoms or solicited events. The subject's parent/guardian will be instructed to contact their primary care provider as soon as possible in the event of worsening respiratory status, recurrence of fever, or for other concerns. Parents/guardians will also be asked to contact study personnel in the event of clinical deterioration (i.e., medical visit or hospitalization for pneumonia) or for any severe solicited events.

Study personnel will be available at each site for urgent issues related to the study or for communication with primary care providers who may have questions about the study.

Subjects who do not meet eligibility criteria or decline consent will be instructed to continue their initially prescribed antibiotic unless otherwise advised by their treating clinician.

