6.5.6. Number of Days of Antibiotic Use at OAV#1 or OAV#2

It will be assumed that all subjects have precisely five days of antibiotic use with the initial antibiotic prior to Day 1 (the day of the first dose of study product). Analysis involving comparisons of the number of days of antibiotic use will consider antibiotic use from Day 1 onwards. The number of days of antibiotic use is defined as the actual number of days of antibiotic use (any amount of study product that is not placebo, or any amount of other systemic antibiotic) from Day 1 to Day 5, inclusive, for OAV#1 and from Day 1 to Day 18 for OAV#2. For subjects that received placebo as study product, it is counted as the number of days of systemic antibiotic as determined solely from the concomitant medication form. For subjects that receive actual antibiotic as study product, it is counted as the number of days that the subject received any amount of either study product or a non-study systemic antibiotic, as determined

from the concomitant medication form. Note that missed doses of study product do not necessarily lower the number of days of antibiotic use as long as a separate dose of antibiotic (study product antibiotic or concomitant medication antibiotic) was received on that day. Extra doses of study product beyond the protocol specification of 10 doses count as normal toward the number of days of antibiotic use. The number of days of antibiotic use is missing (at both OAV#1 and OAV#2) if the product administration record was not completed / on record for the subject and the subject did not have antibiotic use during the study period recorded as a concomitant medication. If a subject does not have an OAV#1 or OAV#2, then number of days of antibiotic use at OAV#1 is missing. If a subject does not have an OAV#2, then number of days of antibiotic use at OAV#2 is missing. As exceptions, subjects that were hospitalized due to pneumonia or a complication of pneumonia or the died during the study period will have number of days of antibiotic use at OAV#1 or OAV#2 as 5 if randomized to the standard course or as 0 if randomized to short course if the number of days of antibiotic use at OAV#1 or OAV#2 is missing as defined above.

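### For a twice-daily child who starts in the afternoon, the protocol's switch instructions give either 9 or 10 prescribed doses, and the dependent day counts are not reconciled

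*Protocol*

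**What the plan says.** **When the prescribed antibiotic starts and stops.** In Protocol section 4, "Day -5 is defined as the date on which oral beta-lactam therapy is initiated for a diagnosis of CAP". The enrollment paragraph of that section states: "Enrolled subjects will continue to receive the initially prescribed antibiotic through Day -1". The intervention paragraph opens in the same way: "Subjects will continue on the initially prescribed antibiotic through Day -1, until they have completed 5 days". Section 7.2 gives the instruction for families: "the subject will be instructed to complete the originally prescribed medication through Day -1". It adds that the last prescribed dose falls on calendar day five of treatment and that study product begins on Day 1, with no time of day.

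**The dose count.** The same sentence of the intervention paragraph equates five days with ten doses of a twice-daily drug. It then works the case of a child whose Day -5 dosing begins in the afternoon: "the first dose of study agent would occur on the afternoon of Day 1, providing 10 total scheduled doses of a twice daily prescribed antimicrobial". SAP section 4.1 repeats this text.

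**Study dosing and the first visit.** Study agent is ten doses, twice daily. Appendix A places its receipt in Days 1-5. The visit is described as "Outcome Assessment Visit #1, Day 6 to 10 (1-5 days after completing the study agent".

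**Counting in the SAP.** Section 6.5.6 states: "It will be assumed that all subjects have precisely five days of antibiotic use with the initial antibiotic prior to Day 1". Section 3.3 starts Day 1 at the clock time of the first study dose, whereas section 6.5 defines Day 1 as a date. Section 6.5.6 counts concomitant antibiotic by date (end minus start, plus one). For children on placebo it takes the count only from the concomitant medication form.

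**The concern.** The trial compares courses of different length, so the point at which prescribed drug gives way to study agent is part of the definition of the intervention. For one group of children, the sentence that defines this point combines a calendar stop with a dose count that cannot both be met. Section 7.2, which governs what families are told, follows the calendar stop alone. Depending on the passage followed, such a child receives nine or ten prescribed doses.

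The example also pushes study dosing into Day 6, which the visit description and Appendix A do not allow for. And it creates a prescribed dose on the date of Day 1, which the SAP's counting rules treat in two different ways. Days of antibiotic use break ties in the primary endpoint, so the SAP should be explicit about such a dose.

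**Working it through.** **Inputs.** Treatment starts on Day -5 (Protocol section 4). There is no Day 0: for a child with no dosing record, SAP section 3.3 sets Day 1 five days after the initiation date, so the days run -5, -4, -3, -2, -1, 1. Assume one morning and one afternoon slot per day, none missed. The example child takes a single dose on Day -5, in the afternoon.

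**Step 1: reproduce the stated 10.** Day -5 afternoon (1) + Days -4 to -1 (4 × 2 = 8) + Day 1 morning (1) = 10. The figure is right for the example, but only with a prescribed dose on the morning of Day 1.

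**Step 2: apply the Day -1 stop.** 1 + 4 × 2 = 9. The gap is one dose: 1/10 = 10% of a ten-dose short course and 1/20 = 5% of a twenty-dose standard course.

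**Step 3: who is affected.** A twice-daily morning starter has 5 × 2 = 10 doses by the end of Day -1 under either rule. A once-daily child has 5 × 1 = 5, as section 4 requires. Only twice-daily children with a single dose on Day -5 are affected.

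**Step 4: end of study dosing.** From Day 1 afternoon, 1 + 4 × 2 = 9 study doses fall in Days 1-5, and the tenth falls on Day 6 morning. From Day 1 morning, 5 × 2 = 10 doses end on Day 5.

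| Twice-daily child | Prescribed doses | Last prescribed dose | Study agent | Day 6 visit: days after completion |
|---|---|---|---|---|
| Morning start, either rule | 10 | Day -1 | Day 1 morning to Day 5 afternoon | 1 |
| Afternoon start, Day -1 stop, study agent from Day 1 morning | 9 | Day -1 | Day 1 morning to Day 5 afternoon | 1 |
| Afternoon start, example | 10 | Day 1 morning | Day 1 afternoon to Day 6 morning | 0 |

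**Step 5: antibiotic days at Visit #1.** Protocol section 6.6 records all current medication. Assume the initial antibiotic is therefore on the concomitant medication form with a Day 1 end date.

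- On the clock definition, the Day 1 morning dose precedes Day 1, so a short-course child has 0 antibiotic days in Days 1-5.
- On the date count, that child has 1.
- A fully adherent standard-course child has 5 either way, because Day 1 already counts through study product.

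The difference is 5 - 0 = 5 or 5 - 1 = 4 days. SAP section 8.3.1 awards the better rank when the difference is at least k days. A difference of 5 wins at k = 1 to 5. A difference of 4 wins at k = 1 to 4 and ties at k = 5.

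**Step 6: Visit #2.** Over Days 1-18, a standard-course afternoon starter on the example schedule has study drug on six dates (Days 1-6), and a morning starter on five. Against a short-course child counted as 1, the differences are 6 - 1 = 5 (still a win at k = 5) and 5 - 1 = 4 (a tie).

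**The case against.** The strongest reply is that section 4 deals with this child expressly: the sentence qualifies the Day -1 stop by completion of ten doses and then works the case. A site that reads the whole sentence gives ten. Under SAP section 3.3's clock, the morning dose precedes Day 1, which fits the SAP's assumption about antibiotic use before Day 1. Both arms follow the same switch rule and receive ten blinded study doses, so the randomized contrast is preserved. Dispensing and administration details are assigned to a manual of procedures that is not among these documents.

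Much of this stands, and it limits the consequences. It does not remove the conflict. Section 7.2 ends prescribed dosing by calendar day, with no exception for afternoon starters, and section 6.5.6's date arithmetic does not follow the clock definition.

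A reader might also infer more than the documents support:

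- **That the short course differs by site.** Nothing ties the choice of rule to site. The text supports variation by time of first dose and by passage followed.
- **That Visit #1 precedes the last study dose.** This needs the example's schedule and a Day 6 visit held before that morning's dose. On schedule it cannot happen on Days 7-10.
- **That an afternoon starter enrolled on Day 1 cannot reach ten doses.** Such enrollment is allowed "provided they have not yet received any doses of the healthcare provider-prescribed antibiotic therapy for that day". That limits doses before enrollment and does not itself bar one afterwards.
- **That bottle collection fails on Day 6.** Sections 7.3 and 7.4 collect the bottle at Visit 2 if available and otherwise at Visit 3.
- **That many children are affected.** The documents give no distribution of first-dose times, so the share is unknown.

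**Conclusion.** The inconsistency is real and narrow. For twice-daily children whose only Day -5 dose is in the afternoon, the protocol supports both nine and ten prescribed doses. Under the example, study dosing ends on Day 6 morning. This contradicts Appendix A, and a Day 6 visit then comes 0 days after completion instead of at least 1.

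The analytic effect is small. If the Day 1 morning dose is on the concomitant medication form and counted by date, the k = 5 exploratory comparison at Visit #1 becomes a tie between such a short-course child and a fully adherent standard-course child with the same ordinal response. The primary tie-break at k = 1 still favors the short-course child (1 day against 5), so the primary analysis is essentially unaffected. The size of the affected group cannot be stated from the documents.

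**What to change.** - **Protocol sections 4 and 7.2, and SAP section 4.1:** reconcile the stop rule, dose count and worked example into one instruction covering morning and afternoon starters, with a dose count that matches its example. Which rule to keep is for the sponsor.
- **Visit 2 description and Appendix A:** align the interval after completion and the study-agent days with that instruction.
- **SAP section 6.5.6:** state that doses of the initial antibiotic taken before the first study dose are not counted in Days 1-5. This settles the clock-versus-date question at Visit #1; the same sentence should cover the Days 1-18 count.

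The cost is a clarifying amendment, matching wording in the family instructions and a sentence in the SAP. It adds no visits or participants and does not change the primary test.
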